5.4.2 HANDLING OF PARTICIPANT WITHDRAWALS OR TERMINATION

Every effort will be made to maintain contact with a subject who withdraws early. If the subject remains at MCC for further care, clinic visits may be tracked and the condition of the subject followed. If the subject is not continuing care at MCC, contact information will be updated at the end of treatment visit, including accurate phone numbers, and email address. The importance of the follow-up period for AEs and SAEs will be stressed to the subject.

All subjects receiving at least 1 day of therapy will be evaluable for safety. Replacement of participants is permitted for those who screen fail or drop out prior to completing initial response assessment at day 28 of treatment, in order to meet the accrual goal of this study.

5.5 PREMATURE TERMINATION OR SUSPENSION OF STUDY

This study may be temporarily suspended or prematurely terminated if there is sufficient reasonable cause. Written notification, documenting the reason for study suspension or termination, will be provided by the suspending or terminating party to investigator, funding agency, the IND/IDE sponsor and regulatory authorities. If the study is prematurely terminated or suspended, the PI will promptly inform the IRB and will provide the reason(s) for the termination or suspension.

Circumstances that may warrant termination or suspension include, but are not limited to:

1. Quality or quantity of data recording is inaccurate or incomplete
2. Poor adherence to protocol and regulatory requirements
3. Incidence or severity of adverse drug reaction in this or other studies indicates a potential health hazard to subjects
4. Plans to modify or discontinue the development of the study drug
5. Determination of futility

In the event Jazz Pharmaceuticals, Inc. decides to no longer supply study drug, ample notification will be provided so that appropriate adjustments to subject treatment can be made.

6 STUDY AGENT

6.1 STUDY AGENT(S) AND CONTROL DESCRIPTION

6.1.1 ACQUISITION

Study agent will be supplied by the manufacturer or IND/IDE sponsor to the Moffitt Research Pharmacy.

6.1.2 FORMULATION, APPEARANCE, PACKAGING, AND LABELING

- CPX-351 (Vyxeos) is stored as a dry powder at 2°C to 8°C
- CPX-351 (Vyxeos) is provided by Jazz Pharmaceuticals.
- CPX-351 is FDA approved and commercially marketed for patients with Acute Myeloid Leukemia
- For this trial we will be using investigational supply for this trial in Acute Lymphoblastic Leukemia.

6.1.3 PRODUCT STORAGE AND STABILITY

Vials of CPX-351 should be refrigerated prior to use (at 2-8°C) and should be utilized prior to expiration as indicated on the individual vials. If reconstituted product is not diluted into an infusion bag immediately, store in refrigerator at 2°C to 8°C for up to 4 hours.

6.1.4 PREPARATION, PRODUCT STORAGE AND STABILITY

The appropriate number of vials of CPX-351 (cytarabine:daunorubicin) Liposome Injection should be removed from the refrigerator, and allowed to equilibrate to room temperature for 30 minutes prior to reconstitution.

Then, reconstitute each vial with 19 mL of Sterile Water for Injection using a sterile syringe and immediately thereafter start a 5-minute timer. Carefully swirl the contents of the vial for 5 minutes while gently inverting the vial every 30 seconds. Do not heat, vortex, or shake vigorously. After reconstitution, let rest for 15 minutes. After reconstitution (but before final dilution), the concentration is 5 u/mL. The reconstituted product should be an opaque, purple, homogeneous dispersion, essentially free from visible particulates. Gently invert each vial 5 times prior to withdrawing the reconstituted product for further dilution. If the reconstituted product is not diluted into an infusion bag immediately, store in refrigerator at 2°C to 8°C for up to 4 hours.

Aseptically withdraw the calculated volume of the reconstituted product from the vial(s) with a sterile syringe and transfer it to an infusion bag containing 500 mL of 0.9% Sodium Chloride Injection, USP or 5% Dextrose Injection, USP. There may be residual product remaining in the vial. Discard unused portion. Gently invert the bag to mix the solution. The dilution of the reconstituted product results in a deep purple, translucent, homogeneous dispersion, free from visible particulates. If the diluted infusion solution is not used immediately, store in refrigerator at 2°C to 8°C for up to 4 hours. Parenteral drug products should be inspected visually for particulate matter and discoloration prior to administration, whenever solution and container permit. Only solutions without visible particles should be used.

The IV bags and infusion sets must be non-DEHP. Aseptic technique must be strictly observed throughout the handling of CPX-351 (cytarabine:daunorubicin) Liposome Injection since no bacteriostatic agent or preservative is present. The infusion of CPX-351 (cytarabine:daunorubicin) Liposome Injection must be started within 4 hours of dilution. Vials are for single use. Unused material should be recorded as such and discarded according to institutional policies. Procedures for proper handling and disposal of anticancer drugs should be implemented.

6.1.5 DOSING AND ADMINISTRATION & ROUTE OF ADMINISTRATION

The infusion of CPX-351 (cytarabine:daunorubicin) Liposome Injection will be performed through a central venous catheter, using an infusion pump to ensure that the drug is infused over the specified time period. Non-DEHP containing administration sets should be used. Do not use an in-line filter. CPX-351 should never be given by the intramuscular or subcutaneous route. Administer CPX-351 over approximately 90 minutes via an infusion pump. Flush the line to ensure administration of the full dose.

The dosage (total units and u/m²), start/stop time of the infusion, total volume infused, must be documented in the patient's chart.

6.1.7 STARTING DOSE AND DOSE ESCALATION SCHEDULE

Patients will receive induction with CPX-351 at a dose of 100 u/m² administered intravenously over 90 minutes on days 1, 3 and 5 of a 28 day cycle.

This may be followed by consolidation with CPX-351 at a dose of 65 u/m² administered intravenously over 90 minutes on days 1 and 3 of a 28 day cycle.

6.1.8 DOSE ADJUSTMENTS/MODIFICATIONS/DELAYS

It is the intention of the study to treat every patient at full dose. Doses may be delayed due to toxicities (for example hypersensitivity reactions). Any doses missed or delayed due to toxicity may be administered as soon as the patient has recovered from the toxicity.

6.1.9 DURATION OF THERAPY

All patients completing induction will be evaluable for efficacy. Consolidation may be started at the time of hematologic recovery (28-75 days after start of induction) for those achieving a complete remission or complete remission with incomplete hematologic recovery. Consolidation cycles may be repeated at the time of hematologic recovery for a maximum total of 3 consolidation cycles.

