7.3.2.10 Induction Day 29 +

- Continuous hospitalization until determined to have acceptable bone marrow recovery
- Laboratory testing continues per standard of care until hospital discharge

7.3.2.11 First Consolidation Therapy Day 1

- Subject has documented response (CR, Cri, or PR, see Appendix A), or in the opinion of the principal investigator is showing clinical benefit with adequate count recovery (ANC > 500/ μ L and platelets > 50,000/ μ L).
- CBC with differential

- Chemistry profile (ALT, AST, alkaline phosphatase, total bilirubin, calcium, bicarbonate, sodium, potassium, chloride, creatinine, BUN, total protein and albumin)
- Day 1 must be given 28 days-75 days after start of induction
- Study drug administration (initiation of CPX-351 intravenously)

7.3.2.12 First Consolidation Therapy Day 3

- CBC with differential
- Chemistry profile (ALT, AST, alkaline phosphatase, total bilirubin, calcium, bicarbonate, sodium, potassium, chloride, creatinine, BUN, total protein and albumin)
- Study drug administration (initiation of CPX-351 intravenously)

7.3.2.13 First Consolidation Day 28

- CBC with differential
- Chemistry profile (ALT, AST, alkaline phosphatase, total bilirubin, calcium, bicarbonate, sodium, potassium, chloride, creatinine, BUN, total protein and albumin)
- LDH, uric acid, magnesium, phosphorus
- Bone marrow biopsy, if bone marrow biopsy is positive at screening
- CT or PET/CT scan of affected areas to assess response for subjects with extramedullary disease

7.3.2.14 Second, and Third Consolidation Therapy Day 1

- Subject has documented response (CR, CRi, or PR, see Appendix A), or in the opinion of the principal investigator is demonstrating clinical benefit with adequate count recovery (ANC > 500/ \square L and platelets > 50,000/ \square)
- CBC with differential
- Chemistry profile (ALT, AST, alkaline phosphatase, total bilirubin, calcium, bicarbonate, sodium, potassium, chloride, creatinine, BUN, total protein and albumin)
- Echocardiogram will be repeated for any patient with >550mg/m² daunorubicin (or daunorubicin anthracycline equivalent) exposure. Therapy will only be permitted if the ejection fraction remains >50% and without >10% decrease in ejection fraction from baseline.
- Day 1 must be given 28 days-56 days after start of the previous consolidation
- Study drug administration (initiation of CPX-351 intravenously)

7.3.2.15 Second and Third Consolidation Day 3

- CBC with differential

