7.3.7 SCHEDULE OF EVENTS TABLE

Procedures: Day:	Screening^a	1	2	3	4	5	6	7	10	28	29+ⁱ	End of Treatment/ Early Term.^g	Follow- Up
Informed consent	X												
Demographics and Medical History	X												
Baseline Symptoms ^b		X											
day Performance Status	X												
Concomitant Medication Review	X	Assess throughout Induction and Consolidation											
Review Adverse Events ^c		Assess throughout Induction and Consolidation										X	
CPX-351 Administration ^d		X		X		X							
Physical Examination	X												
Serum pregnancy test ^e	X												
Vital signs (temp, pulse, resp, BP, weight)	X	X		X		X						Per SOC	
Height	X												
12-lead EKG	X												
Echocardiography/MUGA	X										X ^l		
CBC with differential	X	X	X	X	X	X	X	X	X	X	X	Per SOC	
Serum chemistry testing ^f	X	X	X	X	X	X	X	X	X	X	X	Per SOC	
LDH, uric acid, magnesium, phosphorus	X	X	X	X	X	X	X	X				As needed	
Coagulation studies (PT/INR, aPTT, fibrinogen)	X												
Urinalysis with microscopy	X												
Bone marrow biopsy ^k	X										X		
CT or PET/CT Scan ^m	X										X		
Correlative studies ⁿ	X ^{1,2,3}										X ³		
CSF for ALL involvement/IT chemo ^j	X								X				
Follow-Up													X

- a. Screening assessments will be performed within 28 days of the dose of study drug Day 1. Any standard of care procedure performed within 28 days of Day 1, may be used for screening/eligibility even if performed prior to consent.
- b. Baseline symptoms are defined as those present at the closest time before the start of study drug administration.
- c. Adverse event data will be captured from the time of consent until 30 days after the last dose of CPX-351.

- d. CPX-351 induction therapy will only be administered to a subject following hospital admission. One induction will be administered. Patients with a CR, CRi, PR or determined by the PI to be experiencing clinical benefit after induction, may receive up to 3 consolidation treatments, all administered as an outpatient. First consolidation must be administered no earlier than 35-75 days after day 1 of induction. Second and third consolidations will be administered no earlier than 35-56 days after the start of the previous consolidation.
- e. Serum pregnancy test will be performed on females of childbearing potential (FCBP). A FCBP is considered when a sexually mature female: 1) has not undergone a hysterectomy or bilateral oophorectomy; or 2) has not been naturally postmenopausal for at least 12 consecutive months.

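### The earliest start of consolidation is 28 days in some sections and 35 days in others, for the first cycle and for cycles 2-3

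*Combined protocol and SAP*

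**What the plan says.** First consolidation. Section 6.1.9 permits it at hematologic recovery, "28-75 days after start of induction) for those achieving a complete remission or complete remission with incomplete hematologic recovery". Section 7.3.2.11 makes the same window mandatory: "Day 1 must be given 28 days-75 days after start of induction". The consolidation row of the study schematic gives 35-75 days after the start of induction, although it cites 7.3.2.11 as its source. Footnote d to the Schedule of Events in 7.3.7 reads: "First consolidation must be administered no earlier than 35-75 days after day 1 of induction". Footnote b of Appendix A also sets a 35-day minimum, counted from the last induction course, and does not allow CRi to be declared before Day 35.

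Cycles 2 and 3. Section 7.3.2.14 reads: "Day 1 must be given 28 days-56 days after start of the previous consolidation". Footnote d reads: "Second and third consolidations will be administered no earlier than 35-56 days after the start of the previous consolidation". Section 6.1.9 gives no minimum day here: "Consolidation cycles may be repeated at the time of hematologic recovery for a maximum total of 3 consolidation cycles".

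Who may be consolidated. Section 6.1.9 names CR and CRi. Section 7.3.2.11 is wider: "Subject has documented response (CR, Cri, or PR, see Appendix A), or in the opinion of the principal investigator is showing clinical benefit". Section 7.3.2.14 and footnote d follow the wider rule.

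**The concern.** The interval before the next course of a cytotoxic drug should be a single rule. Here a start 28-34 days after the reference date is expressly allowed by the visit-by-visit text and expressly barred by the footnote to the schedule table, and both use mandatory wording. Section 14.3 treats any noncompliance with the protocol as a deviation and sends deviations to the IRB under its guidelines. The same dose can therefore be recorded as compliant or as a deviation, depending on which page the staff used.

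The interval also bears on a safety matter that the protocol itself singles out. Section 8.4.4 lists failure of marrow recovery after induction or consolidation as an event of special interest. If patients are re-treated at different minimum intervals, the consolidation-phase safety data mix two dosing rules without anyone having chosen to do so. Section 10.4.1 foresees expansion to 19 patients, possibly at several centers, and new sites would have to guess which rule applies.

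**Working it through.** The plan has no computed figure to reproduce on this point. The check sets the texts side by side and counts the days in dispute.

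| Place | First consolidation | Cycles 2-3 | Counted from |
|---|---|---|---|
| 6.1.9 | 28-75 days | no minimum day | start of induction |
| 7.3.2.11 | 28-75 days | – | start of induction |
| 7.3.2.14 | – | 28-56 days | start of previous consolidation |
| Schematic | 35-75 days | – | start of induction |
| 7.3.7, footnote d | not before 35 (35-75) | not before 35 (35-56) | day 1 of induction; start of previous consolidation |
| Appendix A, footnote b | not before 35 | – | last induction course (origin unclear) |

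**Days in dispute.** Days 28 to 34 inclusive: 34 − 28 + 1 = 7 days, for the first consolidation and again for each later interval.

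**Cumulative effect.** The earliest start of the third consolidation is 28 + 28 + 28 = 84 days after the start of induction under the 28-day text, and 35 + 35 + 35 = 105 days under the 35-day text. The difference is 21 days, or 7 per interval.

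**CRi patients.** Section 6.1.9 opens the window to CRi patients at day 28, but Appendix A does not let CRi be declared before Day 35. On a common day count, no patient can qualify as CRi on days 28-34. Section 7.3.2.11 might still admit such a patient through the clinical-benefit route, but 6.1.9 does not mention that route.

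**Origin in Appendix A.** If the 35 days run from day 1 of induction, Appendix A agrees with footnote d. If they run from the last induction dose (day 5, four days after day 1), the floor is 4 + 35 = 39 days after day 1. The text does not say which is meant, so Appendix A is not clean support for any window counted from day 1.

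**Does any text set precedence?** Two come close. The schematic cites 7.3.2.11, which would favor 28 days, but the same row states 35. Section 7.1.1 describes the Schedule of Events as a summary, which would favor the detailed visit sections over footnote d. The 35-day floor also appears outside that table, in the schematic and in Appendix A. Neither text settles the timing.

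**Reach.** The primary endpoint in 4.2.1 is read at day 28 of induction, no later than the earliest consolidation start under either rule. The expansion trigger (4 or more CR/CRi in 10) and the Simon illustration in 10.4.2 take as inputs only the response rates 0.35 and 0.65 and the limits 3 of 10 and 9 of 19. Exact binomial recalculation returns the printed values: probability of early termination 0.514, average N 14.38, alpha 0.084, beta 0.095. No consolidation rule enters.

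**The case against.** The strongest reply is that the windows are nested: 35-75 lies within 28-75, and 35-56 within 28-56. A site that never starts before 35 days satisfies every window counted from day 1, so the protocol can be followed. That is correct, and it is the main reason for choosing 35 as the default. It does not remove the conflict, because the detailed visit sections tell staff that days 28-34 are acceptable.

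A second reply is that the day count is not the only safeguard. Section 6.1.9 requires hematologic recovery. Sections 7.3.2.11 and 7.3.2.14 require a documented response or a judgment of benefit; for later cycles the latter is worded "in the opinion of the principal investigator is demonstrating clinical benefit with adequate count recovery". This stands. A reader might infer that a day-28 start exposes patients to harm, but nothing in the documents shows that day 28 with recovered counts is less safe than day 35. Nor do they say whether anyone has started on days 28-34.

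A third reply is that support for 35 days is uneven. For cycles 2-3 it appears only in footnote d, which is awkwardly worded and sits in a summary table. The Appendix A origin is unclear, and the day-35 rule for CRi gives no reason to delay a patient in full CR. This also stands, so the investigators should confirm the default and not simply have it imposed.

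A reader might also infer that 6.1.9 bars patients in PR from treatment that other sections allow, and that large differences in exposure follow. The documents do not support that. Section 6.1.9 is permissive and never limits consolidation to CR and CRi, 7.3.2.11, 7.3.2.14 and footnote d agree on the wider rule, and the schematic points to 7.3.2.11.

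**Conclusion.** The timing conflict is real, stands in current operative text and is resolved by no precedence rule. It covers 7 days in each interval, for first consolidation and for cycles 2-3, and for CRi patients it is compounded by the Day 35 rule. It should be fixed because it is a dosing rule that is wrong as written, and correcting it is cheap.

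The consequences are limited to when patients are re-treated, how the same dose is classified, and the consistency of the consolidation-phase safety data. A reader might infer that the response result or the expansion decision is compromised. It is not: the choice of window leaves the primary endpoint, the 4-of-10 trigger and the Simon figures as they are. The tension between counting CRi at day 28 (4.2.1) and not declaring it before Day 35 (Appendix A) is a separate matter that this correction does not settle.

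The conclusion assumes that the start of induction and day 1 of induction are the same date. The difference over who may be consolidated is a minor wording mismatch, not a demonstrated contradiction.

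**What to change.** Amend the schematic, 6.1.9, 7.3.2.11, 7.3.2.14, footnote d of 7.3.7 and footnote b of Appendix A to one window with one stated origin. The suggested default is:

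- first consolidation: 35-75 days after day 1 of induction;
- cycles 2 and 3: 35-56 days after day 1 of the previous consolidation.

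This default lies inside every window counted from day 1 and agrees with the Day 35 rule for CRi. The investigators should confirm it, especially for cycles 2-3, where 35 days rests on footnote d alone. If they intend 28 days, the same places need amending in the other direction, and Appendix A must then say how CRi patients are handled before Day 35.

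As a minor alignment, add PR and investigator-judged clinical benefit to 6.1.9 so that it matches 7.3.2.11, 7.3.2.14 and footnote d.

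The cost is amendment wording, with no added patients or procedures. The downside of the default is a start up to 7 days later per interval for patients who recover quickly, so at most 21 days by the third consolidation.

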6.2 STUDY AGENT ACCOUNTABILITY PROCEDURES

The study pharmacist or designee must maintain records of the delivery of CPX-351 to the study site, the inventory at the site, the use by each patient, and the disposition of unused product. These records should include dates, quantities, lot numbers, expiration dates and patient identifications. Institutions should maintain records that document adequately that the patients were provided the doses specified by the protocol and reconcile all investigational product received from the Sponsor. Records of storage conditions (temperature logs) must be kept for the entire period that CPX-351 is maintained at the institution.

7 STUDY PROCEDURES AND SCHEDULE

7.1 STUDY PROCEDURES/EVALUATIONS

7.1.1 STUDY-SPECIFIC PROCEDURES

The Schedule of Events - Section 7.3.7 summarizes the trial procedures to be performed at each visit. Individual trial procedures are described in detail below. It may be necessary to perform these procedures at unscheduled time points if deemed clinically necessary by the investigator.

Furthermore, additional evaluations/testing may be deemed necessary by the PI and/or Jazz Pharmaceuticals for reasons related to subject safety. In some cases, such evaluation/testing may be potentially sensitive in nature (e.g., HIV, Hepatitis C, etc.), and thus local regulations may require that additional consent be obtained from the subject. In these cases, such evaluations/testing will be performed in accordance with those regulations.

7.1.2 STANDARD OF CARE STUDY PROCEDURES

The majority of procedures and laboratory tests on this trial will be performed per standard of care for ALL. Standard of care screening testing will include: bone marrow biopsy, echocardiogram/MUGA, EKG, serum pregnancy test, physical examination, CBC/differential, serum chemistry, vital signs, CSF/IT chemotherapy. During hospitalization, laboratory testing, supportive care measure, and procedures will be following standard of care as for any other ALL treatment.

7.1.3 Informed Consent

Prior to any study procedure that is not considered standard of care, informed consent must be obtained and documented by the subject's dated signature or by the subject's legally acceptable representative's dated signature on a consent form. The dated signature of the person conducting the consent discussion must also appear on the consent form.

7.1.4 Inclusion/Exclusion Criteria

Prior to any trial treatment, all inclusion and exclusion criteria will be reviewed and signed by the PI or Sub-Investigator to ensure the subject qualifies for the trial.

7.1.5 Demographics and Medical History

Demographical information collected will include birth date, age, sex, race, and ethnicity. A medical history will be obtained by the investigator or qualified designee. Medical history will include all active conditions and any condition diagnosed that is considered to be clinically significant by the Investigator. Details regarding the disease for which the subject has enrolled in this study will be recorded separately and not listed as medical history.

